9.2.3 Assessment of other outcomes of interest

Measures of social and community functioning as described in section 5.3.

9.2.4 Assessment of safety outcomes

9.2.4.1 Adverse events

After every rTMS session, participants are asked about new occurrence of adverse events. As example, they are inquired about sensations associated with the stimulation or headaches. The answers are recorded in the CRF. Furthermore, at each study visit during the intervention phase, i.e. after 5 rTMS sessions, patients will be inquired about adverse events using a standard questionnaire in the CRF².

In case the adverse event is not limited to stimulation, the participants will be asked at the next session (24 hours later), whether the adverse event still continues or when it was resolved. The frequency and type of adverse events will be reported in the publication of results.

9.2.4.2 Laboratory parameters

No laboratory parameters will be taken.

9.2.4.3 Vital signs

No routine measurement of vital signs is planned. If patients report dizziness, clinical routines will include measurement of blood pressure and heart rate.

9.2.5 **Assessments in participants who prematurely stop the study**

Participants who prematurely stop the study will be immediately assessed for adverse events. In case of adverse events reports, a physical examination will be conducted and results will be recorded accordingly. Follow-up examinations will be planned within the next 14 days in case of continuing problem related to adverse events, and these examinations will be continued every 14 days until the health issue is resolved.

9.3 **Procedures at each visit**

9.3.1 **Screening visit**

- Check the inclusion and exclusion criteria, use CRF
- Collect demographic data, use CRF
- Conduct urine pregnancy test in female participants between 18 and 50 years of age
- Assess diagnoses with SCID, document results in CRF
- Assess handedness with EHI¹⁰¹, document result in CRF
- Assess medical history in CRF

See table study events at 9.1

9.3.2 **Visit 2 (baseline, week 0)**

- Assess current psychopathology, use PANSS interview and BNSS, document in CRF
- Assess formal thought disorder, use TALD interview, document in CRF
- Assess Neurological soft signs, use NES, document in CRF
- Assess psychiatric history with CASH interview in patients, document result in CRF
- Assess primary outcome with SRRS scale, document in CRF
- Assess motor behaviour with rating scales, use BFCRS, UPDRS, AIMS, document results in CRF
- Assess functioning, use GAF, SOFAS, and UPSA-brief, document results in CRF
- Hand out self-rating questionnaires SNS and IPAQ, collect and document in CRF
- Conduct coin rotation test, record on video
- Record gross motor activity using actigraphy
- Test cortical excitability using the TMS device according to standard procedure. Record electronic data
- Acquire MRI scans at University Institute of Diagnostic and Interventional Neuroradiology
- Acquire posturography at University Hospital, Dept. of Neurology, record electronic data
- Record current medication regime in CRF
- Schedule 5 rTMS sessions
- Schedule next visit

9.3.3 **Visit 3 and 4 (week 1 and 2)**

- Assess primary outcome with SRRS scale, document in CRF
- Assess side effects with questions in the CRF
- Record current medication regime in CRF
- Schedule 5 rTMS sessions
- Schedule next visit

9.3.4 **Visit 5 (end of intervention, week 3)**

- Assess side effects with questions in the CRF

- Assess current psychopathology, use PANSS interview and BNSS, document in CRF
- Assess primary outcome with SRRS scale, document in CRF
- Assess motor behaviour with rating scales, use BFCRS, UPDRS, AIMS, document results in CRF
- Assess functioning, use GAF, SOFAS, and UPSA-brief, document results in CRF
- Hand out self-rating questionnaires SNS and IPAQ, collect and document in CRF
- Conduct coin rotation test, record on video
- Record gross motor activity using actigraphy
- Test cortical excitability using the TMS device according to standard procedure. Record electronic data
- Acquire MRI scans at University Institute of Diagnostic and Interventional Neuroradiology
- Acquire posturography at University Hospital, Dept. of Neurology, record electronic data
- Record current medication regime in CRF
- Schedule next visit (follow-up)

9.3.5 Visit 6 and 7 (follow-up, week 6 and 24)

- Assess current psychopathology, use PANSS interview and BNSS, document in CRF
- Assess primary outcome with SRRS scale, document in CRF
- Assess motor behaviour with rating scales, use BFCRS, UPDRS, AIMS, document results in CRF
- Assess functioning, use GAF, SOFAS, and UPSA-brief, document results in CRF
- Hand out self-rating questionnaires SNS and IPAQ, collect and document in CRF
- Conduct coin rotation test, record on video
- Record gross motor activity using actigraphy
- Test cortical excitability using the TMS device according to standard procedure. Record electronic data
- Record current medication regime in CRF
- Schedule next visit (follow-up)

10. SAFETY

10.1 Medical Device Category A studies

Device deficiencies and all **adverse events (AE)** including all **serious adverse events (SAE)** are collected, fully investigated and documented in the source document and appropriate case report form (CRF) during the entire study period, i.e. from patient's informed consent until the last protocol-specific procedure, including a safety follow-up period. Documentation includes dates of event, treatment, resolution, assessment of seriousness and causal relationship to device and/or study procedure [ISO 14155, 6.4.1.].

Safety is assessed spontaneously at each stimulation session and in a structured set of questions at each visit during the intervention phase (after 5 stimulations). See 9.2.4. If adverse events occur, patients are followed-up with extra-visits after 14 days until the issue has resolved.

Typical adverse events to be expected by rTMS are:

- Mild pain or nausea (39 %)
- Mild headaches (28%)
- Mild neck pain (40%)

Rare events include hearing problems or local skin irritation.

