9.1.1 Patients of treatment groups 1-3

Study Periods	Screening	Treatment, Intervention Period					Follow-up	
		1	2	3	4	5	6	7
Visit								
Time (week)	-1	0	1	2	3	6	24	
Patient Information and Informed Consent	x							
Demographics	x							
CASH and SCID (history)	x							
In- /Exclusion Criteria	x							
Physical Examination	x							
Pregnancy Test	x							
Psychopathology (TALD, NES)		x						
Randomisation		x						
Administer rTMS (5 sessions per week)		x	x	x				
Primary Variable SRRS		x	x	x	x	x	x	
Motor scales UPDRS, BFCRS, AIMS, IPAQ		x			x	x	x	
Psychopathology (PANSS, BNSS, SNS)		x			x	x	x	
Actigraphy and coin rotation		x			x	x	x	
Posturography		x			x			
TMS cortical excitability		x			x	x	x	
Cerebral MRI		x			x			
Functional outcome (SOFAS, GAF, UPSA-brief)		x				x	x	
Concomitant Therapy		x	x	x	x			
Adverse Events		x	x	x	x			

Study events patient groups 1-3

Visit	Information	Instrument used	Expected time
1 (Screening)	Check inclusion / exclusion criteria	CRF	5 min
	Demographic data	CRF	5 min
	Medical history	CRF	10 min
	Handedness	Edinburgh Handedness Inventory ¹⁰¹	5 min
	Pregnancy test	Urine based test	10 min
	Diagnoses ascertainment	SCID interview	60 min
2 (baseline)	Psychopathology	Positive And Negative Syndrome Scale (PANSS) ⁹³ interview, CASH ¹⁰² interview, Brief Negative Symptom Scale (BNSS) ⁹⁴ ,	90 min

		Thought and Language Disorder (TALD) ¹⁰³ , Neurological Evaluation Scale (NES) ¹⁰⁴	
	Primary outcome	SRRS ⁹²	5 min
	Motor scales	Unified Parkinson's Disease Rating Scale (UPDRS) ¹⁰⁵ , Bush Francis Catatonia Rating Scale (BFCRS) ¹⁰⁶ , Abnormal Involuntary Movement Scale (AIMS) ¹⁰⁷	15 min
	Self Report	Self-Evaluation of negative symptoms (SNS) ⁹⁶ , International Physical Activity Questionnaire (IPAQ) ⁹⁵	10 min
	Motor tests	Actigraphy and coin rotation	5 min
	Posturography	Kistler platform at Dept. of Neurology	30 min
	Cortical excitability	TMS paradigm with paired pulse stimulation	30 min
	Neuroimaging	MRI scan including structural T1, Arterial spin labelling, BOLD resting state and task fMRI	60 min
	Functional outcome	Global Assessment of Functioning GAF, Social and Occupational Functioning Scale SOFAS, UPSA-brief assessment of functional capacity	15 min
	rTMS	5 rTMS daily sessions à 20 min	100 min
3 (week 1)	Primary outcome	SRRS	5 min
	rTMS	5 rTMS daily sessions à 20 min	100 min
	Check side effects	CRF	5 min
	Concomitant therapy	CRF	5 min
4 (week 2)	Primary outcome	SRRS	5 min
	rTMS	5 rTMS daily sessions à 20 min	100 min

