11.4.5 Safety analysis

The study team will provide a descriptive analysis of all reported adverse events. The analysis will focus on the type of event, duration, and timing and relate the number of observed events to the number of rTMS sessions administered. Furthermore, the frequency of adverse events will be compared between treatment arms of the trial.

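### Section 10.1 requires adverse events to be collected from consent to the last procedure, but the visit schedules ask about them only during treatment, and the between-arm comparison in 11.4.5 has no window

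*Combined protocol and SAP*

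**What the plan says.** Section 10.1 states that device deficiencies and all adverse events, serious ones included, are collected from consent "until the last protocol-specific procedure, including a safety follow-up period". The length of that safety follow-up is not given.

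Section 9.2.4.1 describes how patients are asked. There is an open enquiry after every rTMS session and, in addition, "at each study visit during the intervention phase, i.e. after 5 rTMS sessions, patients will be inquired about adverse events using a standard questionnaire". The second paragraph of 10.1 limits structured questioning in the same way, and section 5.4 ties the side-effect scale to sessions 5, 10 and 15.

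The grids in 9.1.1 and 9.1.2 mark adverse events at weeks 0, 1, 2 and 3 for groups 1-3, and at weeks 3, 4, 5 and 6 for the waiting group. The follow-up list in 9.3.5 includes "Record current medication regime in CRF" and repeats the excitability testing, but has no side-effect item. The lists for visits 3, 4 and 5 each have one.

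Section 11.4.5 relates events to the number of sessions given and adds that "the frequency of adverse events will be compared between treatment arms of the trial". It names no time window and does not say how the waiting group is handled.

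**The concern.** The collection rule and the visit schedule disagree, and it is the schedule that prompts the question. After the end of treatment the protocol relies on patients volunteering events or on staff learning of them by another route. That matters for three reasons. Section 2.2 expects stimulation effects to persist for 2-4 weeks after the last session, and the safety objective in 4.4 includes the duration of those effects. Patients undergo a further TMS procedure at each follow-up visit, and the definition in 10.1.1 covers events related to procedures. Hospitalisation counts as a serious event, and these patients come mainly from inpatient or day-clinic care, so a readmission during follow-up is a plausible event to ask about.

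In the waiting group it is unclear whether weeks 0-3 are asked about at all. Section 11.4.5 can then be read as comparing all four arms without saying which weeks or which denominator apply.

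**Working it through.** The plan gives no figure on this point, so the check sets the passages side by side and counts weeks.

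| Item | Groups 1-3 | Waiting group |
|---|---|---|
| rTMS given (9.1 grids) | weeks 0 to 3, 15 sessions | weeks 3 to 6, 15 sessions |
| Adverse-event tick (9.1 grids) | weeks 0, 1, 2, 3 | weeks 3, 4, 5, 6 |
| Side-effect check (9.1 event lists) | weeks 1, 2, 3 | weeks 4, 5, 6 |
| Follow-up visits with neither | weeks 6, 24 | weeks 9, 24 |
| TMS excitability testing | weeks 0, 3, 6, 24 | weeks 0, 3, 6, 9, 24 |

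**Coverage.** The span from screening to the last visit is 24 - (-1) = 25 weeks.
- Groups 1-3: covered 3 - 0 = 3 weeks, and 3/25 = 12%. Follow-up without a scheduled question is 24 - 3 = 21 weeks.
- Waiting group: covered 6 - 3 = 3 weeks, again 12%. The waiting period is 3 weeks and follow-up is 24 - 6 = 18 weeks, so 3 + 18 = 21 weeks. If the week-3 tick is taken to look back to week 0, coverage is 6/25 = 24%.
- The screening week is unticked in every group and makes up the balance.

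**Patient-weeks.** With 22 patients per arm, all followed to week 24, unprompted follow-up is 66 × 21 + 22 × 18 = 1,386 + 396 = 1,782 patient-weeks. The waiting period adds 22 × 3 = 66.

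**Possible number of events.** The protocol gives no background rate. At an assumed 0.01 to 0.10 events per patient-week, 1,782 patient-weeks give about 18 to 178 events, and 66 give about 0.7 to 6.6. These are events arising in time without a scheduled question, not events that would go unrecorded.

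**Persistence of effects.** Two to four weeks after the last session is weeks 3 + 2 = 5 to 3 + 4 = 7 in groups 1-3, and weeks 6 + 2 = 8 to 6 + 4 = 10 in the waiting group. The week-6 and week-9 visits fall inside those windows.

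**The week-3 tick.** The note under the study schedule says that the waiting group repeats the visit-2 assessments after 3 weeks and then follows the same protocol. Its ticks at weeks 3-6 are the other groups' ticks at weeks 0-3 moved by three weeks, so its week-3 tick corresponds to a start-of-treatment tick. Section 9.2.4.1 places the questionnaire after five sessions, and none has been given at that point. A look-back over weeks 0-3 is possible but nowhere stated.

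**Evenness between arms.** On treatment, each arm has 3 weeks × 5 = 15 sessions and four grid ticks. Over calendar weeks 0-3, groups 1-3 are asked after each session and weekly, while the waiting group has at most one tick and no sessions, so a per-session rate is undefined there.

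**The case against.** The safety system does not rest on the visit lists alone. Section 10.1 makes whole-study collection mandatory. Serious events must reach the sponsor-investigator within 24 hours of someone learning of them, with no limit to the treatment phase (10.1.2). Known events are followed until resolved, and treating clinicians are contacted if a patient is lost (10.1.3). Section 12.1.1 says that the CRF records side effects and is kept current at each phase, and the CRF itself is an appendix not included in the documents. A reader might infer that follow-up events will be missed. The documents do not support that. What stands is that the reporting and follow-up rules act once an event is known and do not prompt anyone to ask.

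The event lists are also not exhaustive. The baseline list for groups 1-3 omits side effects and concomitant therapy although the grid ticks both, and the week 6 and 24 lists omit the medication record that 9.3.5 requires. A missing line in one list is therefore weak evidence. This carries weight for the waiting group's week 3, where grid and list disagree and the result is ambiguity rather than a proven omission. It carries little for follow-up, where the item is absent from the grids, the event lists and 9.3.5, and where 9.2.4.1 limits the questionnaire to the intervention phase.

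A reader might also infer that the comparison between arms is generally uneven, or that exposure on treatment differs. It does not: lf-rTMS, iTBS and placebo have identical schedules over the same weeks, and the waiting group's treatment period has the same length and number of sessions. Nor is the trial without a reference rate, since placebo is asked about just as intensively and supplies a concurrent background without magnetic pulses.

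Finally, using the waiting group's weeks 0-3 as a formal comparator would set one look-back question against up to 15 post-session enquiries plus weekly questionnaires. It would tend to under-count in the waiting group and exaggerate harm from stimulation. That objection stands and limits the fix.

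**Conclusion.** The inconsistency is real and should be corrected. Section 10.1 requires collection throughout, but scheduled questioning covers 3 of 25 weeks per patient, or 6 of 25 in the waiting group on the most generous reading of its week-3 tick. Events at the follow-up visits are not systematically asked for, including at the visits that fall within the expected persistence of stimulation effects. The waiting group's weeks 0-3 have no defined questioning, and 11.4.5 leaves the window and denominator open.

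The conclusion rests on the grids, lists and sections as printed; a follow-up adverse-event page in the CRF would reduce the gap but not the contradiction. The patient-week totals assume full retention of 88 patients, and the event range rests on an assumed rate. Sample size, error rate and the primary analysis are unaffected. The point does not extend to the contrast among the three immediate-treatment arms, which is even.

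**What to change.** 1. Add the existing adverse-event and side-effect CRF question at weeks 6 and 24 for groups 1-3 and at weeks 9 and 24 for the waiting group. Update the study schedule, the 9.1 grids and event lists, 9.2.4.1 and 9.3.5 to agree with 10.1. Section 9.3.5 names only weeks 6 and 24, so it needs to mention the waiting group's week 9. State in 10.1 how long the safety follow-up period lasts.
2. In the waiting group's week-3 event list, add the question with an explicit look-back to week 0. The grid tick is already there.
3. In 11.4.5, define the between-arm comparison over the on-treatment window (3 weeks, 15 sessions), with lf-rTMS, iTBS and placebo as the concurrent randomised contrast. Report the waiting group's weeks 3-6 separately, per session. Report its weeks 0-3 per patient and descriptively only, because questioning there is less intensive and no sessions are given.

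The cost is about 5 minutes per added question, the time the event lists already allow, at visits that already take place. That is 2 questions × 66 patients + 3 questions × 22 patients = 198 questions, or 198 × 5 = 990 minutes (16.5 hours) over the whole trial at full retention, plus the wording changes.

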10.1.1 Definition and Assessment of safety related events

Adverse Event (AE)

Any untoward medical occurrence, unintended disease or injury or any untoward clinical signs (including an abnormal laboratory finding) in participants, users or other persons whether or not

related to the investigational medical device [ISO 14155: 3.2].

This includes events related to the investigational device or the comparator and to the procedures involved. For users or other persons this is restricted to events related to the investigational medical device.

Adverse Device Effect (ADE)

Adverse event related to the use of an investigational medical device [ISO 14155: 3.1].

This includes any adverse event resulting from insufficient or inadequate instructions for use, deployment, implantation, installation, operation, or any malfunction of the investigational medical device. This includes any event that is a result of a use error or intentional misuse.

Serious Adverse Event (SAE) [European regulation on medical devices 2017/745, art. 58].

Any adverse event that led to any of the following:

- (a) death,
- (b) serious deterioration in the health of the subject that resulted in any of the following:
 - (i) life-threatening illness or injury,
 - (ii) permanent impairment of a body structure or a body function,
 - (iii) hospitalisation or prolongation of patient hospitalisation,
 - (iv) medical or surgical intervention to prevent life-threatening illness or injury or permanent impairment to a body structure or a body function,
 - (v) chronic disease,
- (c) foetal distress, foetal death or a congenital physical or mental impairment or birth defect.

This includes device deficiencies that might have led to a serious adverse event if a) suitable action had not been taken or b) intervention had not been made or c) if circumstances had been less fortunate. These are submitted to the EC via BASEC within 7 days. A planned hospitalisation for pre-existing condition, or a procedure required by the protocol, without a serious deterioration in health, is not considered to be a serious adverse event.

Device deficiency

Inadequacy of a medical device related to its identity, quality, durability, reliability, safety or performance, such as malfunction, misuse or use error and inadequate labelling [ISO 14155: 3.15].

Health hazards that require measures

Findings in the trial that may affect the safety of study participants and, which require preventive or corrective measures intended to protect the health and safety of study participants SAE [ClinO Art. 37].

Causal Relationship of SAE [MEDDEV 2.7/3 revision 3, May 2015].

A causal relationship towards the medical device or study procedure should be rated as follows:

- **Not related:** The relationship to the device or procedures can be excluded.
- **Unlikely:** The relationship with the use of the device seems not relevant and/or the event can be reasonably explained by another cause, but additional information may be obtained.
- **Possible:** The relationship with the use of the investigational device is weak but cannot be ruled out completely. Alternative causes are also possible.
- **Probable:** The relationship with the use of the investigational device seems relevant and/or the event cannot reasonably be explained by another cause.
- **Causal relationship:** The serious event is associated with the investigational device or with procedures beyond reasonable doubt.

Device deficiencies that might have led to an SAE are always related to the medical device.

10.1.2 Reporting of (Serious) Adverse Events and other safety related events

Reporting to Sponsor-Investigator:

The following events are to be reported to the Sponsor-Investigator within 24 hours upon becoming aware of the event:

- All SAEs
- Health hazards that require measures
- Device deficiencies

The Sponsor-Investigator will evaluate SAEs with regard to causality and seriousness. Device deficiencies are assessed regarding their potential to lead to an SAE.

Pregnancies

Because pregnancy tests are a prerequisite to participation and the intervention is only 3 weeks, pregnancies will not be further assessed or reported.

Reporting to Authorities [ClinO Art. 42]:

In Category A studies, the sponsor is subject to the notification requirements specified in Art. 15 of the MedDO of 17 October 2011 (SR 812.213).

It is the Investigator's responsibility to report to the Ethics Committee via BASEC **device deficiencies** that could have led to serious adverse events if suitable action had not been taken, intervention had not been made, or circumstances had been less fortunate within 7 days [ClinO Art. 42].

Health hazards that require measures are reported to the Ethics Committee via BASEC within 2 days [ClinO Art. 37].

Periodic safety reporting:

A yearly safety update-report is submitted by the Investigator to the Ethics Committee via BASEC.

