This study will follow the general recommendations for safety in rTMS protocols^{1, 2} and the device manual. In addition, a screening standard questionnaire for rTMS candidates will be applied to ensure that all strict exclusion criteria for safety in the protocol will be respected. The expected main adverse effects could be transient headache, transient local pain, transient neck pain, transient toothache and transient paraesthesia. Transient hearing changes have not been reported applying theta burst TMS but are likely possible. Therefore hearing protection will be used (earplugs). Furthermore we will make prompt referral for auditory assessment in case of any individual who complains of hearing loss, tinnitus or aural fullness following the rTMS. Seizure induction is rare but possible in epilepsy patients, which are therefore excluded. Furthermore, in some patients transient impairment of working memory was reported. Taken together, if the safety regulations are followed, the risk for participants is minimal. All adverse events are only temporarily occurring and no severe adverse events have been reported in rTMS trials up to now.

Magnetic fields attenuate rapidly with distance, so it seems unlikely that the fetus of a pregnant woman might be directly affected by rTMS. Currently, no side effects to the child were reported in reports of repeated rTMS in pregnant women^{90, 91}. Still, pregnant women will be excluded from this study. Prior to study entry, a pregnancy test will be performed by all women in childbearing age, who are also asked to use a simple, effective contraceptive method during the 3 week trial.

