7.1 Eligibility criteria

Participants fulfilling all of the following **inclusion** criteria are eligible for the study:

- ages 18–60 years
- Right-handed subjects
- Ability and willingness to participate in the study
- Ability to provide written informed consent
- Informed Consent as documented by signature (Appendix Informed Consent Form)

- **Patients only:** schizophrenia spectrum disorders according to DSM-5 **with** psychomotor slowing (SRRS score ≥ 15)

The presence of any one of the following **exclusion** criteria will lead to exclusion of the participant:

- Substance abuse or dependence other than nicotine
- Past or current medical or neurological condition associated with impaired or aberrant movement, such as brain tumors, stroke, M. Parkinson, M. Huntington, dystonia, or severe head trauma with subsequent loss of consciousness.
- Epilepsy or other convulsions
- History of any hearing problems or ringing in the ears
- Standard exclusion criteria for MRI scanning and TMS; e.g. metal implants, claustrophobia
- Patients only: any TMS treatment in the past 3 months
- Women who are pregnant or breast feeding,
- Intention to become pregnant during the course of the study,
- Female participants who are surgically sterilised / hysterectomised or post-menopausal for longer than 2 years are not considered as being of child bearing potential.
- Previous enrolment into the current study,
- Enrolment of the investigator, his/her family members, employees and other dependent persons
- **Controls only:** history of any psychiatric disorder or first-degree relatives with schizophrenia spectrum disorders.

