8.2.2 Control Intervention

Placebo control: 1 Hz stimulation of 17 mins over left SMA without magnetic emission, using the Placebo-coil. 15 sessions in total (5 per week)

Active control: Stimulation parameters for iTBS will follow those of Huang et al.¹⁰⁰, including 600 pulses at 50 Hz (stimulation in 2 sec trains every 10 sec for 190 sec in total). To increase the effect, we will deliver two iTBS series in one session separated by 15 min with a total of 1200 pulses. During the experiment, iTBS pulse intensity is adjusted to 80% of the motor threshold. iTBS stimulation of 21 mins over left SMA, 15 sessions in total (5 per week)

Waiting list: same protocol as active experimental protocol but only between week 3 and 6.

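### The pregnancy test, contraception request and reporting rule do not follow the waiting arm's stimulation window (weeks 3 to 6), and the reporting rule conflicts with the protocol's own SAE definition.

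*Combined protocol and SAP*

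**What the plan says.** Pregnancy is an exclusion criterion (section 7.1). Section 3.7 says: "Prior to study entry, a pregnancy test will be performed by all women in childbearing age", and adds of these women: "who are also asked to use a simple, effective contraceptive method during the 3 week trial". The schedules in sections 9.1.1 and 9.1.2 mark the test once, in the week -1 column. The screening procedure in section 9.3.1 reads: "Conduct urine pregnancy test in female participants between 18 and 50 years of age".

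Section 10.1.2 sets the follow-up rule: "Because pregnancy tests are a prerequisite to participation and the intervention is only 3 weeks, pregnancies will not be further assessed or reported".

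The waiting arm has no intervention in its first three weeks (section 8.1.2). Section 8.2.2 then gives it the "same protocol as active experimental protocol but only between week 3 and 6".

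Among serious adverse events, section 10.1.1 lists "foetal distress, foetal death or a congenital physical or mental impairment or birth defect". Section 10.1 collects all adverse and serious adverse events from consent to the last protocol procedure. Section 10.1.2 requires every SAE to reach the sponsor-investigator within 24 hours of awareness.

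On who can become pregnant, section 7.1 says that women who are surgically sterilised, hysterectomised or "post-menopausal for longer than 2 years are not considered as being of child bearing potential". The same section excludes anyone who intends to become pregnant during the study.

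**The concern.** The pregnancy provisions appear to be written for a patient who is screened, starts stimulation about a week later and finishes at week 3. That describes groups 1-3. One arm in four follows a different calendar, and no passage adapts the test, the contraception request or the reporting rationale to it. For women in that arm, the protocol's own exclusion is checked a month before the first session and not again.

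A second problem does not depend on the arm. Site staff are told to collect and report foetal events as SAEs, and also told not to follow or report the pregnancies through which such events would come to light. Two people reading the safety section could act differently and both be following it.

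What is at stake is participant safety and the completeness of the SAE record. No estimate of efficacy is involved.

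**Working it through.** **1. The plan's own figure.** Sections 8.1.1 to 8.2.2 give 15 sessions at 5 per week. Course length = 15 / 5 = 3 weeks. This holds in all four arms, so the length stated in section 10.1.2 is reproduced.

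**2. Where the course falls relative to the test.** The test is at week -1. Interval = nominal week of stimulation minus (-1).

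| | First rTMS | Test to first rTMS | End of rTMS | Test to end of rTMS |
|---|---|---|---|---|
| Groups 1-3 | week 0 | 0 - (-1) = 1 week | week 3 | 3 - (-1) = 4 weeks |
| Waiting arm | week 3 | 3 - (-1) = 4 weeks | week 6 | 6 - (-1) = 7 weeks |

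The waiting arm's first session comes as long after the test as the end of the course does in groups 1-3. The footnote to the Study Schedule repeats the visit 2 assessments for this arm after the wait. The pregnancy test belongs to visit 1, so the footnote does not bring it back, and the table in section 9.1.2 shows no second test.

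**3. The contraception request.** Section 3.7 gives a duration but no calendar weeks, so two readings are possible for the waiting arm.

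- Weeks 0-3: overlap with stimulation in weeks 3-6 is 0 weeks, so 15 of 15 sessions lie outside the period.
- The patient's own course, weeks 3-6: 0 of 15 sessions lie outside. The three waiting weeks, which fall between the only test and the first session, are then not covered by the request.

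On either reading the wording leaves part of the time from test to end of course unaddressed. On the first reading that part is the stimulation itself.

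**4. How many.** The waiting arm is 22 of 88 patients (22 / 88 = 25%). Both sexes are enrolled (section 7), and only women of childbearing potential are concerned. Their number is not given, so the affected group is an unknown part of 22.

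**5. Foetal events.**

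- Section 10.1.1: foetal events and birth defects are SAEs.
- Section 10.1: all SAEs are collected to the last protocol procedure.
- Section 10.1.2: all SAEs are reported within 24 hours.
- Section 10.1.2, pregnancies: "the intervention is only 3 weeks, pregnancies will not be further assessed or reported".

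The first three create a duty. The fourth removes the means of meeting it in any systematic way. This applies to all 88 patients' arms alike and does not turn on how the three weeks are read.

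**6. Who is tested.** Section 9.3.1 stops testing at age 50, while section 7.1 admits participants to age 60. A woman aged 51-60 who is not sterilised or hysterectomised, and is not more than two years post-menopausal, is of childbearing potential under section 7.1 but is not tested under section 9.3.1.

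**The case against.** The strongest reply is that the protocol says nothing false. The course is three weeks long in every arm, and the contraception request can be read as covering each patient's own course. Section 7.1 excludes women who intend to become pregnant at any time in the study, which reaches past week 6. Section 3.7 gives the protocol's view that a direct effect on a fetus is unlikely. The patient information sheet, listed among the appendices but not available here, may say more. How often to test and how long to ask for contraception are clinical choices.

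Much of this stands. The course length is right, and the contraception gap during stimulation is conditional on one reading. The exclusion for intended pregnancy is relevant, but it rests on a statement made at entry and provides no later check. Section 3.7 keeps the exclusion of pregnant women despite its view of the risk.

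A reader might also infer several stronger things that the documents do not support:

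- That exposure runs to week 24, or 24 - (-1) = 25 weeks after the test. The later TMS is single- and paired-pulse measurement of excitability (section 9.2.2.3), not the rTMS course to which section 10.1.2 refers.
- That foetal SAEs would go uncollected. One that becomes known is still an SAE and still reportable. What is missing is a procedure to find it.
- That all 22 waiting-list patients are affected. Only the women of childbearing potential among them are.
- That a test age limit of 50 is inconsistent in itself with eligibility to 60. Section 3.7 limits testing to women of childbearing age, so only the narrow group in step 6 is left between the two rules.

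**Conclusion.** The point holds in three parts.

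First, the pregnancy provisions do not track the waiting arm's exposure. Stimulation there starts 4 weeks and ends 7 weeks after the only test, with no repeat and no adapted wording. If the contraception period means weeks 0-3, the whole course lies outside it; that condition is an assumption, because the protocol gives no calendar weeks. The intervals use the nominal visit weeks.

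Second, in every arm the SAE definition and collection rules conflict with the statement that pregnancies will not be assessed or reported.

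Third, there is a small mismatch over who is tested between ages 51 and 60.

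This should be corrected. It bears on participant safety and on consistent safety reporting, and has no bearing on sample size, power or the type I error rate. The number of women concerned cannot be derived from the documents.

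**What to change.** Reconcile sections 3.7, 7.1, 9.1.2, 9.3.1, 10.1, 10.1.1 and 10.1.2 so that four items agree:

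- the timing of the pregnancy test relative to each arm's stimulation window;
- the calendar weeks of the contraception request in each arm;
- the population tested, matched to the childbearing definition in use;
- the handling of pregnancies and foetal events, matched to the SAE definition and collection period.

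Which rule to adopt is for the sponsor and the ethics committee; none is proposed here.

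The cost is an amendment to the protocol text, and to the consent wording where it is affected. Any operational cost beyond that depends on the rule chosen. The statistical analysis does not change.
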